Appendix A

Session Fidelity Rating Form

Date of session:

Length of session (timed): _____ min

Treatment visit #:

Randomization group: mPRT

pPRT

Therapists (list all names):

Number of parents present:

1. How many of the stated objectives for the session did the therapist(s) complete?

of objectives met/ # of objectives stated for this session = _____ / _____

2. Was homework assigned from the previous session?

0 = NO

1 = YES

2a. IF YES → Did the therapist(s) review practice/homework assigned in previous session (even if homework was not completed)?

0 = NO

1 = YES

3. Did the therapist(s) explain or preview the session agenda at start of session?

0 = NO

1 = YES

4. How would you describe the therapeutic relationship during the session?

1 = Very poor (e.g., no responding to questions or materials that are posed)

2 = Less than ideal (e.g., partial responding to questions that are posed)

3 = Average (e.g. responds to questions that are posed, seem to understand concepts covered)

4 = Good (e.g., parent asks at least one question or provides elaboration or example, brings up new information or content)

5. Please rate how engaged the caregivers were in the group.

1 = Unengaged

2 = Minimally engaged

3 = Moderately engaged

4 = Actively engaged

Appendix B
mPRT and pPRT Treatment Outline

Wk#	Session	PRT Training Focus	Mindfulness Training Focus	Psycho-education Focus	Worksheets for Homework
Pre	Screening/ Assessment (~2 hr)				
1	Group 1 (2 hr)	Introduction/Administrative; Overview of behavioral treatment approach and PRT (1 hr 15 min)	Overview of ACT components; Define current struggles/difficulties (30 min)	Overview of parent stress research (30 min)	"Play Interest Survey"
2	Group 2 (2 hr)	Detailed review of PRT motivational strategies (1 hr 15 min); Homework review (15 min)	Mindful awareness ("being present") - attention focused (30 min)	Understanding ASD and overlapping conditions (30 min)	"Setting goals for your child" + "Parent values"
	Individual 1 (1 hr)	Individual PRT goals; Demonstrate PRT through therapist-child interactions	Individual check-in on values (10 min)	Individual check-in on info (10 min)	N/A
3	Group 3 (2 hr)	Structured PRT learning opportunities; Natural/incidental learning opportunities	Discuss valued living, committed action and barriers (30 min)	Understanding ASD perspectives (30 min)	"Structured Teaching Brainstorm"
4	Group 4 (2 hr)	In-depth review*: Following the child's lead and shared control	Defusion exercises (30 min)	ASD Interventions I (30 min)	"Maintenance vs. Acquisition"
5	Group 5 (2 hr)	In-depth review*: Maintenance vs. acquisition tasks	Self-compassion (30 min)	ASD Interventions II (30 min)	N/A (plan to revisit child goals during individual session)
6	Midpoint Assessment (30 min) Combine with Individual session				
	Individual 2 (1 hr)	Demonstrate PRT through therapist coached parent-child interactions	Practicing self-compassion before/after session (10 min)	Individual check-in on info (10 min)	"Reinforcing attempts"
7	Group 6 (2 hr)	In-depth review*: Reinforcing reasonable attempts to respond	Incorporating mindfulness into daily life (30 min)	ASD Interventions III (30 min)	N/A
8	Group 7 (2 hr)	In-depth review*: Contingent vs. natural reinforcers	Introduce "self-as-context" or "observing self" (30 min)	ASD Resources: Local/National (30 min)	"Behavior Monitoring Form"
9	Group 8 (2 hr)	Tackling disruptive/problem behaviors	Practicing non-judgment and acceptance attitude (30 min)	Navigating service system (30 min)	N/A (plan to revisit child goals during individual session)
	Individual 3 (1 hr)	Demonstrate PRT through therapist coached parent-child interactions	Apply non-judgment/accepting attitude to interaction (10 min)	Individual check-in on info (10 min)	N/A
10	Group 9 (2 hr)	Planning for future: Child initiations and question asking	Mindful awareness review: emotion focused (30 min)	Neurobiological research (30 min)	N/A
11	Group 10 (2 hr)	Review all PRT points & future target behaviors	Review all material (30 min)	Biomedical Treatment Research (30 min)	"Applying PRT to future situations"
12	Group 11 (2 hr)	Review all PRT points & future target behaviors	Planning for the future (30 min)	Review of all material (30 min)	N/A
12+	Individual 4 (1 hr)	Demonstrate PRT through therapist coached parent-child interactions	Answer questions about material	Answer questions about material	N/A
Post Treatment Assessment					

Appendix C
Utterance Coding Sheet

	1—Unintelligible	2—Imitative (Model Prompt)	3—Verbally prompted	4—Non-verbally prompted	5—Spontaneous	Total Utterances
SLO 1						
						
SLO 4						
Total						

Operational Definitions

1—Unintelligible: The child produces a sound or syllable that is either prompted or unprompted but that is not for a functional purpose or does not constitute an attempt at a meaningful utterance (i.e. “lalalala” or other self-stimulatory repetitious speech)

2—Imitative (model) prompt: The child is responding directly to what the parent has said by imitating or attempts to imitate the word or phrase spoken. For example: Parent: “Ball” Child: “Ball” (or “Baa” or “Buh”) Parent: “I want the ball” Child: “I want the ball” or “I wan Bah”

3—Verbally prompted: The child is responding directly to the prompt given by the parent, such as a fixed-choice prompt (“Do you want the red ball, or the green ball?” “Green ball”), a phrase completion prompt (“One, two, three...” ”GO!”), or an open ended prompt (“What do you want?” “Ball”). The child responds by answering the question or completing the phrase, or provides an expressive verbal attempt to do so.

4—Non-verbally prompted: There is a clear non-verbal prompt from parent, in which they present a clear opportunity by doing something like holding up an item that the child could request, or deliberately pausing an activity and waiting for a response. The child responds with a reasonable attempt to get the desired outcome (i. e. saying “ball” to get the ball the parent is holding up, or “swing” to get to be pushed on the swing again).

5—Spontaneous: There is no intentional verbal or nonverbal effort of the parent or clinician to elicit a response from the child. The child makes a relevant utterance in order to achieve a desired outcome

Appendix D

Fidelity of Implementation Scoring Sheet

	Shared Control		Opportunities to Respond		Interspersing Tasks		Contingent			Attempts
30 second Interval	1. Follow Lead / Choice	2. Identify Natural Reinforcer	3. Attending to the Task	4. Clear Instructions	5. Maintenance	6. Task Variation	7. Natural	8. Immediate	9. Appropriate	10. Attempts
00:00 – 00:30										
9:30-10:00 or end of video clip										
%										
							TOTAL:	%		
* Score each category as (+) or (-)										
* Watch the whole 10 minute sequence, then score each 1 minute interval										
* Score entire 1 minute interval as (-) if no opportunities for language are provided										
* Parents' performance should be independent of child's response.										
* Opportunities for language: Verbal utterances from the parent, produced with the intention of eliciting functional expressive language from the child.										

Operational Definitions:

1. Follow Lead/ Choice: Parent does the following during the entire 30 second interval: follows the child's nonverbal or verbal initiations toward their preferred activity, allows the child to freely select or reject toys from the area, and allows the child to end play with a toy/activity.

2. Natural Reinforcer: During the entire 30 second interval, parent identifies and gains control of preferred object, preferred aspect of an object and/or the aspect of an activity that the child finds most motivating.

3. Attending to Task: During the entire 30 second interval, parent only provides opportunities for language when the child is attending to the task. If child is not attending, parent takes appropriate action to gain child's attention (e.g., covering the toy child is focused on, moving closer to child,

non-verbally enticing with a toy, calling their name, etc.) Attending to the task includes, but is not limited to, child looking at the parent, child looking in direction of parent or object parent is holding, or reaching for object.

4. Clear instructions: During the entire 30 second interval, the parent provides opportunities for language that are short, simple, and related to the task. These opportunities can include, but are not limited to, a verbal model prompt, time delay, offering a choice, and/or asking a question. "Say" can only be used as a prompt under two circumstances: 1) if parent is modeling a replacement behavior (e.g. "Say: 'all done' if you are finished) and/or 2) if the child is stuck in echolalia or is unclear how to respond (e.g. Child says, "What do you want? Ball. Parent models "You can say, 'ball'.") Time delays must be clear as well. Parent should provide a model prompt 3-5 seconds after a time delay if the child cannot respond. Model prompt should maintain object-label correspondence. Recasting and labeling should be distinguishable from model prompts.

5. Maintenance: During the entire 30 second interval, parent clearly balances tasks the child already knows with new tasks. This can include a balance of receptive and expressive tasks. The level of prompts may also be used to balance maintenance and acquisition and should vary based on the motivation of child. If the child is non-verbal or does not have any maintenance tasks, the parent keeps the demands easy for the child (e.g. presenting single syllable, easy to pronounce words).

6. Task Variation: During the entire 30 second interval, parents must use a variety of prompting strategies (e.g., MP, TD, CP, Ch., Q, LS) and/or vary prompting within an activity (not always the same words within the same activity).

7. Natural: During the entire 30 second interval, parent provides a contingent reinforcer that is directly related to the child's expressive verbalizations. A parent scores (-), if they provide an arbitrary reinforcer for the child's expressive verbalization (e.g. child says "ball", parent gives a piece of candy). Parent does not provide reinforcement if the child does not respond.

8. Immediate: During the entire 30 second interval, parent provides primary and/or arbitrary reinforcement just as the child's verbal response is being completed or just after it has been completed (within 2-5 seconds). To be immediate the reinforcement must occur before a second response is made. (must account for intervals where child does not respond or parent is too contingent and no reinforcement is given during entire interval)

9. Appropriate: During the entire 30 second interval, parent never provides reinforcement if the child responds inappropriately. Inappropriate responses can include, but are not limited to, disruptive behaviors and/or self-stimulatory behaviors. Appropriate responses include verbal responses with intent in a clear and calmed voice which includes the child looking in the direction of the adult.

10. Attempts: During the entire 30 second interval, parent provides contingent reinforcement following the child's reasonable verbal attempt, unless otherwise specified (a specific shaping program in place). Reasonable: attending to the item/adult while producing a verbalization, word approximation, or correct word attempt.

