Parent fidelity of PRT implementation (Appendix D). Parent fidelity of PRT

implementation will be coded by trained undergraduate research assistants using *Noldus The Observer XT* to measure changes in level of fidelity in-laboratory semi-structured tasks and in-home naturalistic environments over the course of treatment. All videos, including SLOs at all 4 timepoints as well as weekly videos (averaged for weeks 1-2 and weeks 9-10) will be coded by two research assistants separately (i.e., each research assistant coded all the videos separately). After videos were double-coded, the two research assistants will meet together to complete final consensus coding. All research assistants will attend group training in behavioral coding, behavioral management, and PRT techniques; they will attain at least 80% fidelity with two sample videos coded by PhD and master's level clinicians who were certified in PRT. Standardized measures of PRT fidelity (e.g., Bryson, Koegel, Koegel, Openden, Smith, & Neft, 2007; Minjarez et al., 2011) will be adapted for the current project to accommodate measurement every 30 seconds (as opposed to 1- or 2-minute intervals).

Fidelity of PRT implementation will include 5 total over-arching techniques (i.e., shared control, providing clear opportunities, interspersing maintenance trials, reinforcing attempts, and contingent/natural reinforcement of appropriate behavior), which could be further divided into 10 total components (i.e., following child's lead/child choice, natural reinforcer, attending to task, clear instructions, maintenance, task variation, natural, immediate, appropriate and attempts). The *Noldus* system will be automatically programmed to stop a video after every 30 seconds and prompt the research assistant to input fidelity information for all 10 components in a binary form (i.e., parent either achieved correct performance of component for the entire interval or did not, coded as 1 or 0 respectively). Total correct percentages will be calculated for each component and then averaged over the number of intervals to create a final correct percentage for total PRT

fidelity. Because final percentages will be individually calculated based on the total time they were coded, videos that range in length from 5 minutes to 10 minutes will be used for the current set of analyses.

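### In Appendix D, a parent who follows item 3 while the child is off task for a whole interval scores 0/10, item 3 included, so within-arm fidelity change can be distorted in either direction

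*Combined protocol and SAP*

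**What the plan says.** The Measures section places parent fidelity of PRT implementation under the primary efficacy outcomes. The coding software stops the video every 30 seconds to "prompt the research assistant to input fidelity information for all 10 components in a binary form". A component counts as 1 only if it was performed correctly throughout the interval. Component percentages are then averaged into one total. The published scales were "adapted for the current project to accommodate measurement every 30 seconds (as opposed to 1- or 2-minute intervals"). Clips of 5 to 10 minutes are accepted. No not-applicable code is described.

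In Appendix D, item 3 (Attending to Task) reads "During the entire 30 second interval, parent only provides opportunities for language when the child is attending to the task". It continues "If child is not attending, parent takes appropriate action to gain child's attention", with examples such as moving closer, enticing with a toy without words, or calling the child's name. The scoring notes on the same sheet say "Score entire 1 minute interval as (-) if no opportunities for language are provided" and "Parents' performance should be independent of child's response". They define an opportunity as "Verbal utterances from the parent, produced with the intention of eliciting functional expressive language from the child". Item 4 says "These opportunities can include, but are not limited to, a verbal model prompt, time delay, offering a choice, and/or asking a question".

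Under Group differences, the Statistical Analysis Plan compares fidelity between arms at post-treatment. It also tests change from baseline to endpoint or follow-up within each arm with the Wilcoxon signed rank test.

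**The concern.** Item 3 and the no-opportunity note give opposite instructions for the same behaviour. When the child is off task for an entire interval, item 3 asks the parent to withhold prompts and work on attention. The note then marks that interval as a failure on every component, including the one the parent has just performed correctly. A parent who breaks item 3 by prompting the inattentive child loses item 3 but is still judged on the other nine.

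The total therefore carries a component that belongs partly to the child. If the share of such intervals differs between baseline and post-treatment, or is simply not zero, the recorded pre-post change is not the change in parent skill. Double coding with consensus does not remove this, because both coders apply the same rule.

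**Working it through.** The documents give no expected fidelity, off-task rate or gain, so there is no figure of the plan's to reproduce.

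**1. The text.** Suppose the child is off task for the whole interval and the parent is acting to regain attention.
- Item 3 forbids an opportunity. Calling a name or enticing with a toy is not meant to elicit expressive language, so it does not meet the sheet's definition of one.
- With no opportunity, the note makes the entire interval (-), which is 0/10.
- The nearest thing to an exception is a bracketed reminder under item 8 about intervals in which the child does not respond. It gives no scoring rule.
- If the parent regains attention and prompts once within the interval, the note does not apply.

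**2. Weight of one interval.** A 10-minute clip has 600/30 = 20 intervals, so one blanked interval removes up to 100/20 = 5 points. A 5-minute clip has 10 intervals, so it removes up to 10 points. If the unit is 1 minute, a 10-minute clip has 10 intervals and the loss is also up to 10 points.

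**3. Effect on change.** Let F be percent correct in the other intervals and q the share of blanked intervals. The recorded total is T = F(1 - q). All values of F and q below are assumptions.

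| F before, after | q before, after | T before, after | Recorded gain | True gain |
|---|---|---|---|---|
| 60, 60 | 10%, 5% | 54, 57 | +3 | 0 |
| 60, 60 | 20%, 5% | 48, 57 | +9 | 0 |
| 60, 60 | 30%, 5% | 42, 57 | +15 | 0 |
| 40, 70 | 20%, 5% | 32, 66.5 | +34.5 | +30 |
| 40, 70 | 10%, 10% | 36, 63 | +27 | +30 |
| 40, 70 | 20%, 20% | 32, 56 | +24 | +30 |
| 40, 70 | 5%, 20% | 38, 56 | +18 | +30 |

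With F constant, the false gain is F(q before - q after). For F of 40-80%, q before of 10-40% and q after of 0-10%, it runs from 0 (10% to 10%) to 80 x 0.40 = 32 points. The last row of the table is the case in which parents learn to withhold prompts.

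**4. Interval unit.** The notes say 1 minute. The rows, the item definitions and the Measures text say 30 seconds. As an illustration, take q = p x exp(-L/m), where p is the off-task share of time, m the mean off-task spell and L the interval length. With p = 30% and m = 30 s, q is 11% at 30 s and 4% at 1 minute. Over p = 10-50% and m = 15-60 s, q is 1-30% and 0.2-18% respectively. The unit changes how often the rule applies.

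**5. What the fix does.** Take the same F for every component, and assume the parent is acting to regain attention in every flagged interval.
- *Main score, item 3 exempted:* a flagged interval earns 1 of 10, so T = F(1 - q) + 10q. For F = 60 and q falling from 20% to 5%, T goes from 48 + 2 = 50 to 57 + 0.5 = 57.5, a gain of +7.5. For the true +30 with q constant at 20%, T goes from 34 to 58, still +24.
- *Sensitivity score, items 4-10 also left out of flagged intervals:* T = [7F + 3F(1 - q) + 100q]/10. The first case gives (420 + 144 + 20)/10 = 58.4 and (420 + 171 + 5)/10 = 59.6, a gain of +1.2. The second gives (280 + 96 + 20)/10 = 39.6 and (490 + 168 + 20)/10 = 67.8, a gain of +28.2.

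The exemption corrects item 3. The sensitivity score shows how much of the rest depends on these intervals.

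**The case against.** The best defence is that off-task time is not purely a property of the child. Item 2 asks the parent to gain control of what motivates the child, and item 3 asks for action to regain attention. Failure for a whole interval may be low skill, and the task is to elicit language, so counting an absence of opportunities as failure is defensible. This stands for the other nine items and is why the rule can stay for them in the main score. It does not explain a minus on item 3 for a parent who is doing what item 3 describes.

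The case is also narrow, and that stands too. An interval must contain no opportunity at all, and the sheet defines attending broadly (looking toward the parent or the object, or reaching).

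A reader might infer more than the documents support:
- *That every spell of holding back is penalised.* It is not. One prompt within the interval avoids the blanket minus.
- *That gains are overstated.* This needs such intervals to become rarer for reasons other than parent skill. If they stay constant or increase, gains are understated.
- *That children score better simply because they are used to the room.* The Procedure gives five minutes to get acquainted before the 10-minute elicitation, and home videos are coded as well.
- *That the rule plainly breaks the sheet's own independence principle.* The note says "Parents' performance should be independent of child's response". A response normally follows a prompt and attention precedes it, so the tension is with the spirit of the note more than its words.
- *That the randomised comparison is biased.* Both arms receive the same PRT training and are scored on the same sheet. A chance difference in child attention is sampling variation, which the Mann-Whitney test allows for.

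**Conclusion.** The contradiction is real and stands in the current text. Read literally, the sheet gives a wrong item 3 score, and 0/10 overall, in any interval in which the child is off task throughout and the parent follows item 3. Total fidelity, listed as a primary outcome, therefore depends partly on child attention.

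The weight per interval follows from the documents. The size and direction of the effect on within-arm change do not: they rest on assumed shares of such intervals, and distortion is possible either way. The arm comparison mainly gains noise. Bias there would need a systematic difference between arms in how often these intervals occur, and the documents give no evidence of one.

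**What to change.** Before coding starts:
1. Exempt item 3 from the no-opportunity rule. When the child is off task throughout and the parent is acting to regain attention, score item 3 on its own definition.
2. State one interval unit, reconciling the 1 minute in the notes with the 30 seconds elsewhere. The same edit can settle whether a time delay counts as an opportunity, since the sheet's definition is verbal and item 4 lists a time delay.
3. Flag these intervals and report their number per clip by arm and time point.
4. Keep the no-opportunity rule for the other items in the main score. Add a sensitivity analysis with items 4-10 left out of the denominator in flagged intervals.

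The cost is new sheet wording, coder training and one extra flag in software programmed for binary entry. Coders must judge attention in intervals with no prompt. The sensitivity score rests on fewer intervals and may be lenient to parents who fail to re-engage the child, which is why it should not replace the main score.

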Appendix F

Parent Feelings Questionnaire (Deater-Deckard, 2000)

Every parent experiences both positive and negative feelings toward his or her child. Listed below are statements describing some of these feelings that parents may experience. Read each statement carefully and circle the number that most closely reflects your feelings toward your child: **1 = definitely untrue for you**, to **5 = definitely true for you**. Try to provide an answer for each item without skipping or looking back.

Think about your child, and use this scale when circling the appropriate number for each item:

1	2	3	4	5
Definitely untrue for me	Somewhat untrue for me	Not really true for me	Somewhat true for me	Definitely true for me
I usually make an effort to praise my child for good behavior.				1 2 3 4 5
Sometimes I am not happy about my relationship with my child.				1 2 3 4 5
Every once in a while my child's behavior can bring out the worst in me.				1 2 3 4 5
Every once in a while I avoid talking or playing with my child, such as when I am angry with her/him				1 2 3 4 5
I enjoy hugging and cuddling with my child.				1 2 3 4 5
Sometimes I find it difficult to be around my child.				1 2 3 4 5
My child and I do not get along as I had hoped we would.				1 2 3 4 5
Most of the time, my child brings out the best in me.				1 2 3 4 5
Sometimes I do not enjoy being with my child.				1 2 3 4 5
My child and I fight or argue more than I would like to.				1 2 3 4 5
I enjoy being my child's parent.				1 2 3 4 5
Every once in a while I wish that my child would just go away for a few minutes.				1 2 3 4 5
Sometimes my child's behavior makes me so angry I can barely stand it.				1 2 3 4 5
Being around my child is more enjoyable than I ever thought it would be.				1 2 3 4 5
Every once in a while I feel some resentment toward my child.				1 2 3 4 5
Sometimes I do not get along well with my child.				1 2 3 4 5
I am usually affectionate with my child.				1 2 3 4 5
I find it easy to praise and compliment my child, especially for good behavior.				1 2 3 4 5
Sometimes I do not enjoy spending time alone with my child.				1 2 3 4 5
Sometimes I find it difficult to communicate with my child.				1 2 3 4 5
When I think about my child, it usually gives me warm feelings.				1 2 3 4 5
Sometimes I raise my voice with my child, especially after I've had a bad day.				1 2 3 4 5
Sometimes my child can really test my patience.				1 2 3 4 5
I usually feel quite happy about my relationship with my child.				1 2 3 4 5

